9.5	Clinical Trial Insurance and Compensation to Subjects.....	44
9.6	Independent Ethics Committee or Institutional Review Board	44
9.7	Health Authorities.....	44
10	Trial Management	44
10.1	Case Report Form Handling	45
10.2	Source Data and Subject Files	45

10.3	Investigator Site File and Archiving.....	46
10.4	Monitoring, Quality Assurance and Inspection by Health Authorities	46
10.5	Changes to the Clinical Trial Protocol.....	46
10.6	Clinical Trial Report and Publication Policy.....	47
10.6.1	Clinical Trial Report	47
10.6.2	Publication	47
11	References Cited in the Text.....	47
	Signature Page – Protocol Lead.....	50
	Signature Page –Coordinating Investigator	51
	Signature Page – Principal Investigator	52
	Sponsor Responsible Persons not Named on the Cover Page.....	错误!未定义书签。

List of Abbreviations

ADR	Adverse drug reaction
AE	Adverse event
AFC	Antral follicle count
ART	Assisted reproductive technology
β -hCG	Beta-human chorionic gonadotropin
COS	Controlled ovarian stimulation
CRO	Contract research organization
eCRF	Electronic case report form
ET	Embryo transfer
FET	Frozen embryo transfer
E ₂	Estradiol
FSH	Follicle stimulating hormone
Gn	Gonadotropin
GnRH-a	Gonadotropin-releasing hormone agonist
GnRH-ant	Gonadotropin-releasing hormone antagonist
hCG	Human chorionic gonadotropin
iCOS	Individualized controlled ovarian stimulation
ICSI	Intracytoplasmic sperm injection
IEC	Independent Ethics Committee
IRB	Institutional Review Board
IU	International Unit
IVF	In vitro fertilization
LH	Luteinizing hormone
MII	Metaphase II
OHSS	Ovarian hyperstimulation syndrome
PCOS	Polycystic ovary syndrome
r-LH	Recombinant luteinizing hormone
r-FSH	Recombinant human follicle stimulating hormone
SAE	Serious adverse event
SmPC	Summary of product characteristics

1 Synopsis

Clinical Trial Protocol Number	MS700623_0020
Title	A prospective, randomized controlled study to investigate the cumulative live birth rates (CLBRs) of gonadotrophin-releasing hormone (GnRH) antagonist protocol compared with the standard GnRH agonist long protocol for controlled ovarian stimulation in supposed normal ovarian responders
Trial Phase	Phase IV
IND Number	Not applicable
FDA covered trial	No
EudraCT Number	Not applicable
Principal Investigator	Peking University Third Hospital
Sponsor	Center for Reproductive Medicine, Peking University Third Hospital
Sponsor Legal Representative in the European Union	Not applicable
Trial centers/countries	This study will be conducted in approximately 5 centers in China
Planned trial period (first subject in-last subject out)	About 34 months
Trial Registry	Register study information on ClinicalTrials.gov

Objectives:
 
Primary objectives
 
 • To investigate the cumulative live birth rates in infertile women ≤ 38 years old with normal ovarian reserve using GnRH antagonist or agonist protocol for COS in ART treatment 
Secondary Objectives
 
 • To investigate the safety and pregnancy outcomes of GnRH antagonist and agonist protocols after the fresh embryo transfer 	

Methodology:
 
This is a Phase IV, prospective, randomized controlled study to investigate the cumulative live birth rates (CLBRs) of gonadotrophin-releasing hormone (GnRH) antagonist protocol (GnRH-ant group) compared with the standard GnRH agonist long protocol (GnRH-a group) for controlled ovarian stimulation in supposed normal ovarian responders.
	

CELEBRATE Study

MS700623_0020

In this study, patients who are planning to undergo IVF/ICSI cycle aged ≤ 38 years old with normal ovarian reserve will be considered for enrollment. Approximately 888 patients will be enrolled at approximately 5 centers in China over a period of 10 months.

About 12-20 visits will be performed in this study for each patient.

The CLBR with first live birth resulting from one initiated COS cycle will be compared between GnRH-a group and GnRH-ant group.

Planned number of subjects: 888

Primary endpoints:

CLBR with first live birth resulting from one initiated COS cycle

Secondary endpoints:

- Number of oocytes retrieved
- Good-quality embryo rate (The Istanbul Consensus²⁹)
- hCG positive rate
- Implantation rate
- Clinical pregnancy rate
- Ongoing pregnancy rate
- Live birth rate
- Cumulative clinical pregnancy rate
- Miscarriage rate
- Ectopic pregnancy rate
- Cycle cancelled rate and reason
- Rate and severity of OHSS
- Time to pregnancy
- Time to live birth

Pharmacokinetics: Not applicable

Other assessments:

To explore the relationship between the number of oocytes retrieved and number of embryos or times of embryo transfer or CLBR

Diagnosis and key inclusion and exclusion criteria:

Diagnosis: Infertile women planning to undergo IVF/ICSI cycle aged ≤ 38 years old with normal ovarian reserve

Inclusion criteria:

1. Infertile women planning to undergo IVF/ICSI cycle using conventional GnRH agonist long protocol or GnRH antagonist protocol
2. Age ≤ 38 years old
3. Basal AFC 8~20
4. Basal FSH ≤ 10 IU/L
5. Basal E₂ < 200 pmol/L

6. Normal uterus and at least one side of the normal ovary
7. Informed consent form signed
8. Willing to follow the study protocol, and able to complete this study

Exclusion criteria:

1. Previous IVF/ICSI cycles >2
2. Severe hydro-salpinx (Ultrasound shows hydro salpinx > 2cm)
3. Severe endometriosis (Grade III – IV)
4. Polycystic ovarian syndrome (PCOS)
5. History of recurrent miscarriages (>2 times of miscarriages)
6. Plan to undergo ovarian stimulation for preimplantation genetic diagnosis or preimplantation genetic screening, oocyte donation, and social or medical freezing of oocytes
7. Any major systemic disease that as per Investigator's discretion precludes subject for participation in the study
8. With pregnancy contraindications
9. Alcoholism, drug abuse, drug addiction or patients with uncured sexually transmitted disease
10. According to the judgment of the Investigator, any medical condition or any concomitant surgery/medications that would interfere with evaluation of study medications
11. Simultaneous participation in another clinical study
12. Plan to use urinary gonadotrophin during COS treatment

Investigational Medicinal Product:

GnRH-a group: The GnRH-a (Diphereline[®] or Decapetyl[®]) 0.1mg will be administered for about 14 to 20 days for down-regulation. Recombinant FSH (Gonal-f[®]) will be administered as routinely practiced by investigators. GnRH-a types, GnRH-a and FSH doses will be adjusted according to the clinical experiences of investigators in each site.

GnRH-ant group: Recombinant FSH (Gonal-f[®]) will be administered as routinely practiced by investigators. FSH doses will be adjusted according to the clinical experiences of investigators. The GnRH-ant (Cetrotide[®]) will be initiated in a fixed protocol on stimulation days 5 or 6 per the investigator's ART protocol.

Reference therapy:

LH supplementation: If there is slow/suboptimal response in follicular development observed by investigators, the rLH (Luveris[®]) will be administered as required. LH supplementation is based on one of the following criteria¹ :

- Having no follicle >10 mm by day 6;
- Low estradiol concentration <200 pg/ml or <732 pmol/L by day 6;
- Poor progression or slowing of follicle growth, i.e., previously 1–2 mm progression/day slowing to less than 2 mm in 3 days.

Planned trial and treatment duration per subject:

Two years (from the administration of FSH)

Statistical methods:

For this non-inferiority trial, a sufficient number of subjects will be enrolled to have at least 80% power to demonstrate the non-inferiority of GnRH antagonist protocol vs GnRH agonist protocol regarding the CLBR using a two-sided 95% confidence interval. The CLBR is expected to be 60% in both groups, and the non-inferiority margin is -10% (absolute). Based on these assumptions, a sample size of 377 evaluable subjects per arm would provide 80% power to demonstrate the non-inferiority of GnRH antagonist protocol vs GnRH agonist protocol regarding the CLBR. As a result, totally about 888 subjects will be randomized, that is 444 for each treatment group after considering 15% dropout rate.

The primary analyses will be performed on the PP population, and will be confirmed on the ITT. Safety analysis will be based on the safety population.

In general, continuous variables will be presented with number of subjects, mean, standard deviation, median, minimum, and maximum. Categorical variables will be presented with number and percentage of subjects within each specific category.

The result of the analysis of the primary endpoint (CLBR) is essential for the non-inferiority claim. The conservative CLBR will be used to test the hypothesis in a confirmatory way. Conservative CLBR with the corresponding 95% confidence interval (CI) will be based on binominal distribution. The two treatments will be compared by using Chi-square test for conservative CLBR. The difference between the two treatments and its associated 95% CI based on asymptotic normal distribution will be presented. If the lower-limit of the 95% confidence interval is greater than the non-inferiority limit (-10%), the null hypothesis will be rejected and it would be claimed that GnRH antagonist protocol is non-inferior to GnRH agonist protocol regarding to the cumulative live birth rate.

Optimal CLBR will be analyzed using Kaplan-Meier product-limit method, the rate and its 95% CI will be provided. For optimal CLBR, the two treatments will be compared using Kaplan-Meier product-limit estimates, the difference between the two treatments and its associated 95% CI will be also presented.

The analyses of the secondary rate endpoints will use the same methods as the conservative CLBR and the analysis of secondary time-to-event variables will use the similar methods as the optimal CLBR, which are intended to provide additional characterization of the treatment effect.

Number of oocytes retrieved will be summarized and compared basing on analysis of variance (ANOVA) including treatment and center as factors. The treatment difference and the two-sided 95% confidence interval will be reported.

Furthermore, univariate/multivariate logistic or cox regression analysis will be performed to evaluate the dependence of Age (≤ 35 or > 35 years), AFC, AMH, number of oocytes retrieved, number of usable embryos, times of embryo transfer, and BMI in relation to pregnancy rate or CLBR.

Table X Schedule of Assessments

Procedure Visit	Screening/Baseline	Gn Initiation	Triggering Day	Oocytes pick up	Embryo Transfer		HCG Test	Clinical pregnancy assessment	Ongoing Pregnancy (fresh cycle)	Live Birth	End of Observation	2 years Follow up Visit
					fresh cycle	FET						
Demography	x											
Medical history	x											
Inclusion and exclusion criteria	x											
Signed informed consent form	x											
Physical examination and vital signs	x											
Clinical and gynecological examination	x											
FSH levels within last 3 months	x											
E ₂ level within last 3 months	x											
AMH*	x											
AFC within last 3 months	x											
Administration of GnRH-a (long protocol group)		x	x									
Administration of Gonal-f® new pen		x	x									
Administration of GnRH-ant (GnRH-ant protocol group)			x									
LH levels		x										
r-LH supplementation if need			x									
HCG trigger			x									
E ₂ level		x										
Oocytes pick up				x								

CELEBRATE Study

MS700623_0020

Procedure Visit	Screening/Baseline	Gn Initiation	Triggering Day	Oocytes pick up	Embryo Transfer		HCG Test	Clinical pregnancy assessment	Ongoing Pregnancy (fresh cycle)	Live Birth	End of Observation	2 years Follow up Visit
					fresh cycle	FET						
Embryo transfer					x	x						
Pregnancy assessment by serum β -hCG test							x					
Clinical Pregnancy assessment by ultrasound scan						x		x				
Ongoing pregnancy									x			
Live birth										x		
Safety												
OHSS			x	x								
AEs		x	x	x	x		x	x	x	x		
Concomitant medication		x	x	x	x		x	x	x	x		

* After randomization.

After each embryo transfer in the fresh cycle / frozen embryo transfer (FET), HCG test, clinical pregnancy assessment, ongoing pregnancy (only in the fresh cycle) and live birth assessment should be performed and recorded.

2 Sponsor, Investigators and Trial Administrative Structure

This clinical trial will be sponsored by: Center for Reproductive Medicine, Peking University Third Hospital

The trial will be conducted at about 5 sites in China.

The Principal Investigator ([name], Peking University Third Hospital), represents all Investigators for decisions and discussions regarding this trial, consistent with the Good Clinical Practice (GCP). The Principal Investigator will provide expert medical input and advice relating to trial design and execution and is responsible for the review and signoff of the clinical trial report.

Signature pages for the Principal Investigator as well as a list of Sponsor responsible persons are in Appendix 1.

It is planned to perform the study at approximately 5 sites across China. A Contract Research Organization (CRO) will be appointed for the conduct of the trial (including trial management, monitoring, data management, statistical analysis and medical writing).

3 Background Information

In the last 50 years, development of assisted reproduction and unprecedented success has given hope to couples who were considered sub-fertile and constituted 10-15% of the general population. In the developed nations 1% of the children are thought to be conceived with the help of assisted reproductive technology (ART) (Larcher V, 2007). Since the birth of Louise Brown, first "test tube baby", more than five million babies have been born worldwide with the help of ART (Qiao J, 2014). Joint research and collaboration between diversified scientific fields like biology, physiology, endocrinology, embryology, laboratory science and clinical medicine resulted in development of ART of today (Feinberg EC, 2005). Howard and Jones in USA and Trounson from Australia pioneered COH (controlled ovarian hyperstimulation) by using gonadotropins derived from the urine and provided a useful tool for in vitro fertilization (IVF) (Trounson AO, 1981. Brinsden PR, 2009; Zhao Y, 2011). These injectable gonadotropins made it possible to expose ovarian follicles to higher hormonal levels and make a larger number of ovarian follicles to mature into oocytes which can be retrieved predictably in a large number from a single IVF cycle (Zhao Y, 2011).

Higher number of oocytes retrieved has been linked with greater chances of pregnancy (Fleming R, 1996) and will increase the efficacy and efficiency of the reproductive treatment. This is done by hyper stimulation of the ovaries by external recombinant gonadotrophins (Commenges-Ducos M, 1998. Macklon NS, 2006). Average number of follicles recruited in an ovarian stimulation cycle have risen to ten, twenty or more, which have led to the yield of enhanced number of oocytes per cycle (Edwards RG, 1996). Manipulation of menstrual physiology with the help of drugs and surgery is the key to success in ART (Matzuk M, 2008).

In clinical practice, the most common used protocols in controlled ovarian stimulation include the long protocol (GnRH-a will be used) and short protocol (GnRH-ant will be used). GnRH analogues are given to the women undergoing ovarian hyper-stimulation to obviate LH surge which may

cause the follicles to ovulate prematurely. In order to suppress internal secretion of pituitary gonadotropin, GnRH agonists are used which help in revolutionizing the process and procedure of stimulation of the ovaries and prevention of LH (luteinizing hormone) surge. GnRH agonists utilize agonistic analogues of gonadotropins which have some amino acids substitutions in their amino acid sequence which happen to make them more competent and enhance their half lives in comparison with the natural hormones. GnRH agonists provide release of gonadotropin secretion (Copperman AB, 2013), but after 5-7d continuous application, the pituitary is no longer respond to the stimulation then become desensitization, achieve the down-regulation (JING X, 2012). So called long protocol consist of giving external gonadotropin along with GnRH agonists and causing suppression of pituitary FSH and LH. By this protocol cancellation rate is reduced and there is increase in recruitment of the follicles and getting larger number of oocytes. The incidence of premature surges of LH is also remarkably reduced. Ovarian stimulation, through the use of GnRH agonists, helps to improve pregnancy rate as a result of IVF (Macklon NS, 2006). GnRH antagonists cause sudden chemical suppression of the pituitary, thereby causing shutdown of LH (luteinizing hormone) and FSH (follicle stimulating hormone) secretion (Shrestha D, 2015). GnRH antagonists are given in the mid-cycle which prevents an early LH surge (Gordts S, 2010). No suppression occurs in the beginning of follicular phase which is an important time for recruitment of the follicles. Ovarian stimulation by GnRH antagonist protocol is not only short but also cost effective (Depalo R, 2012). Perfect synchronization of female endocrines, endometrial physiology and embryonic factors form the basis of molecular communication between the uterine endometrium and upcoming embryo which helps in implantation and subsequent conception (Cartwright JE, 2010). Changes in morphology of the endometrium and hormonal secretion ensure proper embryo transfer and implantation capable of progression to pregnancy (Gellersen B, 2014).

Both GnRH agonist and GnRH antagonist protocols are widely used in controlled ovarian stimulation (COS); however, there is a persistent debate concerning the reproductive outcomes when comparing the two analogue treatments (Toftager M, 2016). In the most recent Cochrane review, the GnRH antagonist protocol was associated with comparable live birth rate (LBR) and a substantial reduction in the incidence of OHSS when compared to GnRH agonist long protocol in women undergoing ART in none selected population (Hesham G AI,2016).

Comparing with GnRH agonist protocol, the GnRH antagonist protocol is associated with fewer oocytes retrieved, lower OHSS incidence whereas the ongoing pregnancy rate and LBR were similar in supposed normal responders in the recent systematic review and meta-analysis (JS Xiao, 2014). However, the data published in the same year found that among good-prognosis patients, agonist protocol decreased cancellation risk and increased odds of implantation and live birth compared with antagonist protocol using the national surveillance data (D. Grow, 2014).

Overall, there is an ongoing debate regarding the superiority of these two COS protocols in supposed normal responders.

In the other aspect, IVF success has generally been calculated and reported on the basis of LBRs per treatment attempt involving either an intended fresh or frozen-thawed embryo transfer (FET). The continued improvement in reproductive technology has seen an increase in the number of FETs and their associated pregnancy rates. This, combined with an emphasis on reducing multiple pregnancies and increasing single embryo transfers (SETs), means that outcomes per fresh embryo transfer are no longer meaningful to patients and clinicians who want to know their chance of live birth over an entire IVF program. The most appropriate way of reporting this is to estimate the

cumulative chances of success per woman after a number of complete cycles—defined as all fresh and FET attempts resulting from one episode of ovarian stimulation. CLBRs are increasingly proving to be the currency of IVF (DJ. McL 2016).

From fertility counselling perspective, patients undergoing IVF treatments should be informed not only the opportunity of success rate in fresh cycle transfer but also the probability to achieve a live birth after utilization of all cryopreserved embryos.

The retrospective data from Peking University Third Hospital showed that the CLBR was about 50% in unselected population (unpublished data). The CLBR was about 60% with 11-15 oocytes retrieved in Chinese population from retrospective published data (Jingjuan J, 2013).

The latest published data regarding the CLBRs of these two protocols in a prospective study showed comparable results (34.1% in the GnRH-antagonist group vs 31.2% in the GnRH-agonist group) in unselected population (Toftage M., 2017). However, the CLBR in this study was just a secondary endpoint and it is much lower than the data expected in Chinese population.

In China, there is no prospective randomized study so far to compare the CLBR between GnRH-antagonist protocol and GnRH-agonist protocol in COS. Local study and data generation is in need to provide more evidence regarding to these two protocols to guide the clinicians in their daily practice and also provide valuable data for patients counselling.

4 Trial Objectives

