8.3.2 Secondary Endpoints

COS and pregnant outcomes, including:

- Number of oocytes retrieved
- Good-quality embryo rate(The Istanbul Consensus1)
- hCG positive rate (in fresh cycle)
- Implantation rate (in fresh cycle)
- Clinical pregnancy rate (in fresh cycle)
- Ongoing pregnancy rate(in fresh cycle)
- Live birth rate(in fresh cycle)
- Cumulative clinical pregnancy rate
- Miscarriage rate(in fresh cycle)
- Ectopic pregnancy rate(in fresh cycle)
- Cycle cancelled rate and reason(in fresh cycle)
- Rate and severity of OHSS(in fresh cycle)
- Time to pregnancy
- Time to live birth

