8.5.3 Analysis of Secondary Endpoints

Definition of some important secondary endpoints:

Clinical pregnancy: a pregnancy diagnosed by ultra-sonographic visualization of one or more gestational sacs or definitive clinical signs of pregnancy. It includes ectopic pregnancy. Note: Multiple gestational sacs are counted as one clinical pregnancy.

Clinical pregnancy rate: the number of clinical pregnancies expressed per 100 initiated cycles, aspiration cycles, or embryo transfer cycles. Note: When clinical pregnancy rates are given, the denominator (initiated, aspirated, or embryo transfer cycles) must be specified.

Cumulative clinical pregnancy rate: Numerator is the No. of women got their first clinical pregnancy, the Denominator is the No. of women who attempt the ovarian stimulation.

Live birth rate: Numerator is the No. of women got live birth resulting from fresh cycle (multiple births considered as one live birth), the Denominator is the No. of women who attempt the ovarian stimulation.

Implantation rate: the number of gestational sacs observed divided by the number of embryos transferred.

Ongoing pregnancy: intrauterine pregnancy continued for 12 gestational weeks (detection of presence of gestational sac with fetal heartbeat by transvaginal ultrasound examination in week 12).

Time to pregnancy: time from Gn Initiation to the first clinical pregnancy.

Time to live birth: time from Gn Initiation to the first live birth.

Cancelled cycle: an ART cycle in which ovarian stimulation or monitoring has been carried out with the intention to treat, but which did not proceed to follicular aspiration or, in the case of a thawed embryo, to embryo transfer.

Miscarriage, also known as spontaneous abortion and pregnancy loss, is the natural death of an embryo or fetus before it is able to survive independently

The analysis of the secondary endpoints are intended to provide additional characterization of the treatment effect.

Number, time, percentages and related CIs will also be reported for the following secondary endpoints:

- Number of oocytes retrieved
- Good-quality embryo rate(The Istanbul Consensus1)
- hCG positive rate (in fresh cycle)
- Implantation rate (in fresh cycle)
- Clinical pregnancy rate (in fresh cycle)
- Ongoing pregnancy rate(in fresh cycle)
- Live birth rate(in fresh cycle)
- Cumulative clinical pregnancy rate
- Miscarriage rate(in fresh cycle)
- Ectopic pregnancy rate(in fresh cycle)
- Cycle cancelled rate and reason(in fresh cycle)

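### Implantation rate is defined per embryo transferred, but the synopsis gives it the per-woman CLBR methods, so its CI is too narrow if some women receive two embryos and their outcomes are positively correlated

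*Combined protocol and SAP*

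**What the plan says.** The Synopsis (Statistical methods) describes the conservative CLBR analysis: a binomial CI for each arm, a chi-square test, and then "The difference between the two treatments and its associated 95% CI based on asymptotic normal distribution will be presented". Section 8.5.2 repeats these methods and makes the woman the unit in both numerator and denominator. The synopsis then extends them without exception: "The analyses of the secondary rate endpoints will use the same methods as the conservative CLBR".

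Implantation rate is a listed secondary endpoint, limited to the fresh cycle in sections 8.3.2 and 8.5.3. Section 8.5.3 defines it with a different unit: "Implantation rate: the number of gestational sacs observed divided by the number of embryos transferred". On analysis, that section says only "Number, time, percentages and related CIs will also be reported for the following secondary endpoints". It names no method, so it neither repeats nor replaces the synopsis rule. On purpose, it says "The analysis of the secondary endpoints are intended to provide additional characterization of the treatment effect".

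Section 7.2.5 records how many embryos were transferred. No section states, caps or predicts that number. Section 7.2.8 provides for recording multiple pregnancy. No section mentions clustering, robust variance, GEE, mixed models or a bootstrap.

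**The concern.** Binomial and chi-square methods assume that the counted units are independent. That is reasonable for CLBR, with one result per woman. It is not reasonable for embryos transferred together, which share a mother, an endometrium and a stimulation cycle. If the synopsis rule is followed with embryos as the denominator, 377 women with two embryos each are treated as 754 independent observations. With positive correlation within women, the variance is understated, the CI for the arm difference is too short, and the chi-square test rejects too often. What is at stake is the stated precision of one supportive endpoint, which readers may set beside the main result when judging endometrial receptivity or embryo competence between protocols.

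**Working it through.** **The plan's own figure.** The sample size concerns CLBR only (60% in both arms, margin 10 points, two-sided 95% CI, 80% power; section 8.1). n = 2 × 0.6 × 0.4 × (1.96 + 0.8416)² / 0.10² = 376.7, so 377 per arm. 377 / 0.85 = 443.5, so 444 per arm and 888 in total. This reproduces and is not in dispute. The documents give no figure for implantation rate.

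**Inputs assumed, because the documents do not give them.** Implantation rate 0.4; ICC within a woman 0.1 to 0.4; transfers all double, 60% double with 40% single, or all single; 377 women per arm with a fresh transfer (the CLBR evaluable number, borrowed as an upper case) or 250, since section 7.2.5 allows for women with no fresh transfer.

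**Design effect.** For a ratio of totals with m embryos per woman, DE = 1 + ICC × (Σm²/Σm − 1).
- All double: Σm²/Σm = 4/2 = 2, so DE = 1 + ICC, or 1.10 to 1.40.
- 60/40 mix: mean m = 1.6 and mean m² = 0.6 × 4 + 0.4 × 1 = 2.8. The ratio is 1.75 and DE = 1 + 0.75 × ICC, or 1.075 to 1.30.
- All single: DE = 1 at any ICC.

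**Consequences.** The correct width is the stated width × √DE. Coverage of the nominal 95% CI is 2Φ(1.96/√DE) − 1, and the type I error of the nominal 5% test is its complement.

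| Transfers | Correct CI wider by | Coverage | Type I error |
|---|---|---|---|
| All double | 5–18% | 93.8–90.2% | 6.2–9.8% |
| 60/40 mix | 4–14% | 94.1–91.4% | 5.9–8.6% |
| All single | 0% | 95% | 5% |

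**Half-width of the CI for the difference.** The stated value is 1.96 × √(2 × 0.4 × 0.6 / embryos per arm).

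| Women per arm | Transfers | Embryos per arm | Stated (points) | Correct (points) |
|---|---|---|---|---|
| 377 | All double | 754 | 4.9 | 5.2–5.9 |
| 377 | 60/40 mix | 603.2 | 5.5 | 5.7–6.3 |
| 250 | All double | 500 | 6.1 | 6.4–7.2 |
| 250 | 60/40 mix | 400 | 6.8 | 7.0–7.7 |

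**Simulation check** (beta-binomial, no true difference, 377 women per arm, rate 0.4, 20,000 replicates). At ICC 0.1, 0.2, 0.3 and 0.4 the unclustered CI covered 93.8, 92.7, 91.7 and 90.2% with all double transfers, and 93.9, 93.0, 92.3 and 91.2% with the mix. A ratio estimator with variance clustered on woman covered 94.7–95.2% in every setting tried. A separate run at rate 0.35 with all double transfers gave 94.1, 92.7, 92.0 and 89.3% for the unclustered CI at ICC 0.1, 0.2, 0.3 and 0.5.

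**Which GEE matches the defined ratio.** Suppose 40% of women have a single transfer at rate 0.50 and 60% a double transfer at 0.35. The defined ratio is (0.4 × 0.50 + 1.2 × 0.35) / 1.6 = 38.75%. One unweighted row per woman gives 0.4 × 0.50 + 0.6 × 0.35 = 41.0%. An exchangeable working correlation of 0.1 to 0.4 gives 39.0–39.8%. Only independence with embryo-level rows, or with weights equal to embryos transferred, returns 38.75%.

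**The case against.** The best defence is that no sentence says embryos will be entered as independent trials. The rule is one general line in a synopsis, most secondary rates do have one outcome per woman, and section 8.5.3 names no method, so the plan might be called merely silent on implantation rate. It is true that 8.5.3 is silent. But the synopsis line has no exception, is the only rule available, and gives an unclustered CI when applied to the defined ratio. Section 8.5.1 defers to the Statistical Analysis Plan only for missing data.

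A second defence is that the size rests on assumptions. This stands in full. Section 3 even notes a move towards single embryo transfer, the case with no effect. That remark does not bind the sites, and the plan records embryo numbers and multiple pregnancies. At the low end (mix, ICC 0.1, 377 women) the half-width moves only from 5.5 to 5.7 points. No secondary endpoint carries a decision rule, so the type I error figures matter little in practice.

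Two stronger readings are tempting, and the documents do not support them:
- A reader might infer that good-quality embryo rate has the same fault on a larger scale, since a woman has more embryos than are transferred. The plan does not define that rate's denominator, so no size can be given.
- A reader might infer from "Multiple gestational sacs are counted as one clinical pregnancy" that, with no such rule for implantation, sacs could outnumber embryos transferred. That does not follow. The rule is needed whenever two transferred embryos both implant; an excess of sacs would need a further event, such as embryo splitting, which the plan does not mention.

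**Conclusion.** The point holds as a fault in the stated method, not merely a missing detail. The direction is certain under two conditions: some women receive more than one embryo, and outcomes within a woman are positively correlated. The size is modest and cannot be fixed from the documents; the ranges above rest wholly on the assumed rate, ICC and transfer mix. If implantation were also counted over frozen transfers, which the Synopsis and section 7.3.2 do not exclude, clusters and the understatement could be larger, but sections 8.3.2 and 8.5.3 restrict it to the fresh cycle. It would be wrong to infer any threat to the non-inferiority claim: the CLBR test, the −10 point margin and N = 888 do not depend on this endpoint. It is a low-priority correction worth making.

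**What to change.** 1. In the synopsis and section 8.5.3, restrict the borrowed CLBR methods to secondary endpoints with one binary outcome per woman.
2. For implantation rate, keep the defined ratio of total sacs to total embryos transferred in each arm. Take the difference and its 95% CI from a bootstrap that resamples women within arm, or from a ratio estimator with variance clustered on woman. If a GEE is preferred, specify an identity link, independence working correlation, and embryo-level rows or weights equal to embryos transferred. Drop the unclustered chi-square test for this endpoint.
3. State the denominator of good-quality embryo rate. If it is per embryo, use the same clustered variance.

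The cost is SAP wording and a few lines of code. The number of embryos transferred is already collected. Section 7.2.8 lists presence of sac(s) and singleton or multiple pregnancy, so confirm that the eCRF holds a sac count per woman, which the endpoint needs under any method. The downside is a slightly wider CI for a supportive endpoint. Visits, sample size and the primary analysis do not change.
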